#### 14.3.1 Safety Parameters

Parameters	Value
Best-corrected visual acuity	No change of 1 line in the Snellen chart or 1 logarithmic point (logMAR)
Intraocular pressure	Measurements below 7 mmHg and over 21 mmHg
Corneal depithelization	Percentage of the damaged epithelium of the ocular surface, reduction of staining according to the Oxford scale.
Anterior segment examination	Abnormalities on any of the comprised structures: Cornea, iris, pupil, iris-corneal angle and crystalline.
Posterior segment examination	Abnormalities on any of the comprised structures: Vitreous, retina, macula and optic nerve.
Tear film break-up time	Reduction of more than 20% over the baseline time.
Schirmer test	Reduction of more than 20%
Adverse events	Presence of adverse events modifying some of the abovementioned criteria or others evaluated as serious.
OSDI	Increase of the score of more than 10 points.

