### 13.1 TBUT

The sample size was calculated according to the formula for continuous quantitative variables:

$$n=2 \left[ \frac{(Z_{\alpha} - Z_{1-\beta})(\delta)}{d} \right]^2$$

With a statistical confidence level of 95%, which corresponds to error type I, and is equal to 1.96, with a potency of 80% corresponding to error type II, and is equal to 0.84, a standard deviation for an increase in TBUT of 1.1 seconds was considered, with an expected difference of at least 0.15 seconds.

Based on the above, the result was 32 patients per group, which increased 20% in consideration of the losses, with a total of 39 patients per group, with a total study population of 116 subjects (232 eyes).

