### 13.2 OSDI

The sample size was calculated according to the formula for continuous quantitative variables:

With a statistical confidence level of 95%, which corresponds to the error type I, and is equal to 1.96, with a potency of 80% corresponding to the error type II, and is equal to 0.84, a standard deviation for the 6.4 points increase in score OSDI, with an expected difference of at least 6.1 points, was considered.

Based on the above, the result was 34 patients, which increased 20% in consideration of the losses, with a total of 41 patients per group, with total study population of 123 subjects (246 eyes).

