### 13.3 Schirmer

The sample size was calculated according to the formula for continuous quantitative variables:

With a statistical confidence level of 95%, which corresponds to the error type I, and is equal to 1.96, with a potency of 80% corresponding to the error type II, and is equal to 0.84, a standard deviation for the 1.72 mm/5 min increase in the Schirmer test, with an expected difference of at least 0.13 mm/5 min, was considered.

Based on the above, the result was 80 patients, which increased 20% in consideration of the losses, with a total of 96 patients per group, with total study population of 288 subjects (576 eyes).

Based on the above calculations and considering the primary outcome variable, and Schirmer test used in the study to demonstrate efficacy between the 3 groups, the total population to evaluate will be of 288 subjects.

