#### 14.2.1 Tolerability Parameters

Parameters	Value
Burning	It should be recorded as absent on 95% of the evaluated subjects
Foreign body sensation	It should be recorded as absent on 95% of the evaluated subjects
Tearing	It should be recorded as absent on 95% of the evaluated subjects
Secretion	It should be recorded as absent on 95% of the evaluated subjects
Conjunctival hyperemia	
The following must be accomplished:
 
 
• Absent: <math>\geq 95.0\%</math>
 
• Mild: <math>\leq 5.0\%</math>
 
• Moderate: <math>\leq 2.5\%</math>
 
• Serious: <math>\leq 1.0\%</math>
 

Photophobia	
The following must be accomplished:
 
 
• Absent: <math>\geq 95.0\%</math>
 
• Mild: <math>\leq 5.0\%</math>
 
• Moderate: <math>\leq 2.5\%</math>
 
• Serious: <math>\leq 1.0\%</math>
 

Safety variables of the study drug PRO-087 will be evaluated in the visits indicated in the schedule, using the following parameters:

1. Best-corrected visual acuity
2. Intraocular pressure
3. Ocular surface
4. Anterior segment exploration
5. Posterior segment exploration
6. Tear film break-up time
7. Schirmer test
8. Corneal depithelization
9. Adverse events

It is considered that the drug in evaluation PRO-087 is tolerable for use in human beings, if there are not changes on the marked parameters (14.3.1) by more than 5% of subjects, in both eyes, in compliance with all visits and adherence to treatment at an  $\geq 80\%$  during the time of study assessment.

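### The 5%-of-subjects safety verdict has no comparator, named visit or allowance for variability, so a product with no effect could fail it, most plausibly on Schirmer

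*Combined protocol and SAP*

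**What the plan says.** The verdict follows the list of nine safety variables after the tolerability table in section 14.2.1. PRO-087 is acceptable "if there are not changes on the marked parameters (14.3.1) by more than 5% of subjects, in both eyes", among subjects who comply with all visits and take at least 80% of treatment. The limits are in section 14.3.1: for TBUT, "Reduction of more than 20% over the baseline time"; for Schirmer, a fall of more than 20%; for OSDI, "Increase of the score of more than 10 points".

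No visit is named beyond those in the schedule. No comparator or confidence limit enters the verdict, and neither the limits nor the 5% are justified.

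The only variability figures are in section 13: "a standard deviation for an increase in TBUT of 1.1 seconds", "a standard deviation for the 6.4 points" for OSDI, and "a standard deviation for the 1.72 mm/5 min" for Schirmer.

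Two internal mismatches bear on the point:
- OSDI is in the 14.3.1 table but not in the list of nine safety variables, although section 13 treats it as one of three main safety variables.
- Schirmer is scheduled at Visit 2 in section 9 but is absent from the Visit 2 procedures in section 11.3.

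**The concern.** An absolute 5% limit in one arm works only if few subjects would cross by chance. If ordinary variation alone carries about 5% across, the verdict says little about the drug. It can then fail a harmless product, and the same data can pass or fail according to which visits are counted. The two randomised comparator arms would show the background crossing rate, but the verdict does not refer to them.

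**Working it through.** **1. The plan's own figures.** Section 13 uses n = 2[(z-sum)(SD)/d]² with 1.96 and 0.84. The formula is printed with a minus sign; the usual sum is 2.80.
- TBUT: 2(2.80 × 1.1/0.15)² = 843, against 32 stated.
- OSDI: 2(2.80 × 6.4/6.1)² = 17.3, against 34 stated.
- Schirmer: 2(2.80 × 1.72/0.13)² = 2,745, against 80 stated.

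The stated sizes are not reproduced. The literal minus sign gives 135, 2.8 and 439, which do not match either. Solving SD = d√(n/2)/2.80 from the stated n gives 0.21 s, 8.98 points and 0.29 mm. The printed SDs are therefore uncertain inputs.

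**2. Inputs for the check.** SDs 1.1 s, 6.4 points and 1.72 mm (section 13), read as SDs of change. Baselines 5 to 10 s and 4 to 14 mm (section 12.1). There are 80 evaluable or 96 enrolled per arm (section 13.3). Since 5% of these is 4 and 4.8, five or more subjects breach the rule in either case.

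Assumptions not in the documents: changes normal with mean zero, baselines spread evenly, inter-eye correlation 0.5 to 0.8.

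**3. One eye (or one score), one visit: P(Z > limit/SD).**
- OSDI: 10/6.4 = 1.56, giving 5.9%.
- Schirmer: 0.8/1.72 = 0.47 at 4 mm, 32%; 1.8/1.72 = 1.05 at 9 mm, 14.8%; 2.8/1.72 = 1.63 at 14 mm, 5.2%. Averaged over baselines, 16%.
- TBUT: 1.0/1.1 = 0.91 at 5 s, 18.2%; 1.5/1.1 = 1.36 at 7.5 s, 8.6%; 2.0/1.1 = 1.82 at 10 s, 3.5%. Averaged, 9%.

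**4. Both eyes, one visit.** This is a simulation with the eyes' baselines correlated like their changes; the last column is the binomial chance of five or more crossing. OSDI is one score per subject, so the both-eyes condition does not affect it.

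| Measure | Crossing, r = 0.5 | Crossing, r = 0.8 | Chance of failing, 80 to 96 subjects |
|---|---|---|---|
| Schirmer | 6.3% | 9.9% | 58% to 97% |
| TBUT | 3.0% | 5.2% | 9% to 57% |
| OSDI | 5.9% | 5.9% | 51% to 68% |

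If the two eyes' Schirmer baselines are unrelated, the rate at r = 0.5 is 5.9% and the lower failure figure is 51%. At r = 0.3, from a baseline of 9 mm, the Schirmer rate is about 4%. With independent eyes it is about 3% (0.16² = 2.6%, or 3.2% if both eyes share a baseline).

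**5. If a crossing at any of four visits counted.** OSDI with independent visits: 1 − (1 − 0.059)⁴ = 22%; with between-visit correlation 0.8, 12%. Schirmer in both eyes at the same visit, between-visit correlation 0.5: 17% to 25%.

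**6. Sensitivity to the meaning of the SDs.** If they are cross-sectional, the SD of change is SD√(2(1 − r)), with r the baseline-to-visit correlation. The one-eye or one-score rate falls below 5% once r exceeds about 0.55 (OSDI), 0.66 (TBUT at 7.5 s) or 0.80 (Schirmer at 9 mm). With the SDs back-solved in step 1, Schirmer and TBUT crossings are almost nil and OSDI is P(Z > 10/8.98) = 13%.

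**The case against.** The strongest objection is to the inputs. Section 13 can be read as giving the size of an increase rather than its SD. The values come from cited studies, may include real differences in response, and do not reproduce the stated sample sizes. So a reader might infer that the limits lie within measurement noise, but the documents do not support this: they give no test-retest error. This objection stands, and the result is therefore conditional.

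Three other readings are tempting but not supported.
- **All three measures would fail.** TBUT in both eyes at one visit is at or near the limit rather than clearly over it. Section 12.2.3 also removes subjects whose TBUT falls below 5 s, and any fall of more than 20% from a baseline up to 6.25 s lands there (0.8 × 6.25 = 5). If either eye below 5 s removes the subject, the simulated both-eyes rate at the final visit among those kept is about 1% to 2%.
- **Failure is near certain because there are four visits.** The plan does not say that a crossing at any visit counts.
- **The comparator arms are unused.** Section 15 plans between-group tests. It is the pass/fail verdict that lacks a comparator.

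A real improvement also lowers the rates: with a mean OSDI fall of 6.1 points, (10 + 6.1)/6.4 = 2.52 SD, or 0.6%. That is true, but a safety rule should also behave sensibly for a product with no effect.

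**Conclusion.** The point holds in conditional form, as something that should be changed. The verdict is uncontrolled, names no visit and makes no allowance for variability. With the section 13 figures read as SDs of change and an inter-eye correlation of 0.5 to 0.8, a no-effect product would more likely than not fail on Schirmer (about 6% to 10% crossing; 51% to 97% chance of failing with 80 to 96 subjects). OSDI is borderline at one visit and well over the limit (12% to 22%) only if any of four visits counts. TBUT failure is possible but not expected, even before eliminations. Nearly independent eyes, or cross-sectional SDs with high baseline-to-visit correlation, would bring the rates below 5%. The dependence on an unstated visit rule and the missing comparator remain whichever SD reading is right.

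**What to change.** For Schirmer, OSDI and TBUT, base the safety conclusion on the proportion of subjects crossing each listed limit in PRO-087 minus that in each comparator, with 95% CIs, at a named main visit (for example day 90).
- Tabulate the other visits by arm so that early signals are kept.
- Make the subject the unit, with an explicit both-eyes rule for Schirmer and TBUT; OSDI is already one score per subject.
- State how eliminated subjects are counted. The verdict is worded for subjects compliant with all visits, while section 17.4 keeps the available data of withdrawn patients for safety analysis.
- Keep the listed limits as descriptive thresholds, and say what the section 13 SDs measure.
- Reconcile OSDI between the safety list and 14.3.1, and Schirmer at Visit 2 between sections 9 and 11.3.

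The data are already planned, so the cost is SAP wording and a few tables. The downside is losing a simple absolute pass/fail. The intervals are also wide: with 80 per arm and about 6% crossing in each, 1.96√(2 × 0.06 × 0.94/80) is roughly ±7 percentage points.

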## 15. Proposed statistical analysis.

---

The statistical analysis will be performed by an investigator blinded to the intervention groups.

The continuous quantitative variables will be presented by measures of central tendency and dispersion (mean, standard deviation and ranges). Nominal and ordinal qualitative variables will be introduced by means of frequencies and ratios.

The Kolmogorov-Smirnov test will be performed to know the normal or abnormal distribution of the results obtained in each study group.

Assuming there is a normal distribution of data, the intra-group differences will be determined by an ANOVA test for repeated measures, with the Pearson correlation coefficient, for the quantitative variables.

For qualitative variables the  $\chi^2$  (chi square) test will be used and in case the expected frequencies are less than 5 the Fisher's exact test will be used.

The differences between groups will be analyzed using the ANOVA test for variance analysis, with the Pearson correlation coefficient, for the qualitative variables.

For qualitative variables, contingency tables 2x2 will be used and the differences will be calculated with  $\chi^2$  (chi square) with Yates's correction and in case the expected frequencies are less than 5 the Fisher's exact test will be used.

The significance level will be of a 0.05 alpha value or less.

The final statistical analysis will include all the subjects that complete the visits listed in the activity chronogram.

Also, those who have been assigned with a treatment (intervention) and attend at least to 1 visit after the baseline will be included and analyzed until the moment they attended.

Those who do not attend at least 1 follow up visit will be excluded.

Those who do not complete the visits will be classified as population with intention to treat.

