### 12.2.3 Elimination criteria for the subject included on the study

1. Signs and symptoms evolving to serious tear film dysfunction syndrome detected on any treatment visit.
  - a. TBUT < 5 seconds
  - b. Peripheral or secondary leucoma to corneal scarring
  - c. Phlycten
  - d. Corneal keratinization
  - e. Epithelial squamous metaplasia
  - f. Corneal conjunctivalization
  - g. Corneal neovascularization
  - h. Corneal ulcers
  - i. Any secondary injury permanently reducing the visual acuity, as a consequence of the tear film dysfunction.
2. Added ocular surface diseases requiring a different treatment to PRO-087 or added treatments indicated for a new diagnose.
3. Opacities on ocular clear media (cornea, lens, vitreous body) avoiding to assess the anterior chamber or the posterior segment.
4. Decision of the subject
5. Difficulty to attend the follow-up appointments.
6. Added or self-prescribed non-authorized treatments
7. Herbal treatments affecting the course of the disease or producing other complications not related with the disease
8. Systemic diseases requiring an immunomodulator, immunosuppressing or biological treatments affecting any inflammatory cascade line.

9. Retinal diseases secondary to chronic-degenerating diseases requiring treatment to preserve the function and/or anatomy
10. Inflammatory retinal diseases
11. Uveitis presentation installation at any ocular uveal level
12. Clinical picture meaning an ophthalmic urgency requiring immediate treatment
13. Ocular diseases requiring surgical treatment
14. Ocular diseases requiring intraocular injections

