### *17.4 Patient elimination*

The causes for a withdrawal of the study from a patient might be the following:

Subject's decision. The patient who wishes to leave the study for any reason can do so at any time, but the investigator must be informed of this. In all cases, the investigator must try to get in contact with the patient as soon as possible for a final assessment in order to do the following:

Document the patient's decision in clinical notes,

Obtain the reason(s) of the departure and record them in the departure form of the CRF,

Assess the clinical state of the patient,

If necessary, take the appropriate therapeutic measures: management of an adverse event or concomitant disease.

Investigator's decision: Especially if there is an adverse event and if the investigator considers that this might threaten the patient's health, actions will be taken as described on the adverse events section or if there is an important disease that needs the prescription of a drug incompatible with the purpose of the study. It will be reported in clinical notes and a serious adverse events report format will be filled and the Research Ethics Committee, the clinical monitor and Pharmacovigilance of Laboratorios Sophia will be informed of this.

A wrongful inclusion according to the protocol. The decision to keep the patient in the will be taken conjointly by the investigator and the sponsor.

Other reasons (insufficient response, need for another treatment).

In all cases, the available data will be kept for safety analysis (assessable population for intention to treat).

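### Section 15 promises to analyse partial attenders, but the repeated-measures ANOVA it names for within-group change cannot, in its classical form, use them; completers may then overstate improvement

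*Combined protocol and SAP*

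**What the plan says.** All the analysis rules are in section 15. For change within a group, "the intra-group differences will be determined by an ANOVA test for repeated measures". Between groups, "The differences between groups will be analyzed using the ANOVA test for variance analysis"; that sentence attaches the test to qualitative variables, evidently a slip for quantitative ones. It names no visit.

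On who is analysed, section 15 makes three statements:
- "The final statistical analysis will include all the subjects that complete the visits listed in the activity chronogram".
- Subjects who were assigned a treatment and "attend at least to 1 visit after the baseline will be included and analyzed until the moment they attended".
- "Those who do not complete the visits will be classified as population with intention to treat".

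No imputation, mixed model or other rule for missing visits appears anywhere. Section 17.4 keeps leavers' available data for safety analysis.

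Two other places govern who leaves. Section 12.2.3 eliminates subjects who evolve to serious disease at any treatment visit (its first item is TBUT below 5 seconds) and also lists "Added or self-prescribed non-authorized treatments". Section 17.4 gives as causes of withdrawal "Other reasons (insufficient response, need for another treatment").

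**The concern.** The inclusion promise and the named within-group test do not fit together. A subject who stops after day 30 has three of the five scheduled values. Section 15 says this subject is analysed up to that point, but the classical repeated-measures ANOVA has no place for an incomplete series. The analyst would have to choose a missing-data rule after the data exist.

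The choice matters because leaving is partly driven by outcome. TBUT is an efficacy variable (section 14.1) and also a ground for elimination, and insufficient response is a listed cause of withdrawal. If poor responders leave and the test keeps only completers, the reported within-arm change looks better than it was. For OSDI, where improvement is a fall, the fall is overstated. Within-arm change from baseline is what specific objective 5.2.3 and the thresholds in section 14.1.2 rest on.

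**Working it through.** **1. What each named test can use.** Section 9 schedules days 1, 7, 30, 60 and 90.

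| Subject | Promise in section 15 | Classical repeated-measures ANOVA | ANOVA between groups at one visit |
|---|---|---|---|
| Attends all five visits | included | used | used at every visit |
| Last attended day 30 | included up to day 30 | dropped | used at days 7 and 30, absent at days 60 and 90 |
| No post-baseline visit | excluded | dropped | not used |

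The conflict is in the second row. It is complete for the within-group test. For a visit-by-visit group comparison it applies only at the visits missed, including day 90.

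**2. How many subjects.** Section 13.3 takes 80 per group and adds 20%: 80 × 1.20 = 96, and 96 × 3 = 288. Both steps reproduce. The allowance is 96 − 80 = 16 per arm, so 16/96 = 16.7%, or 48 of 288 in all.

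**3. Selection bias in closed form.** Let *d* be the fraction lost and ρ an assumed correlation between the tendency to leave and poor change. With z = Φ⁻¹(d),

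bias in completers = ρ · φ(z) / (1 − d), in SD units.

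At d = 0.167: z = −0.967, φ(z) = 0.250, and 0.250/0.833 = 0.300. The SDs are those in sections 13.1 and 13.3.

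| ρ (assumed) | Bias, SD | TBUT (SD 1.1 s) | Schirmer (SD 1.72 mm) |
|---|---|---|---|
| 0 | 0 | 0 | 0 |
| 0.2 | 0.060 | 0.07 s | 0.10 mm |
| 0.5 | 0.150 | 0.17 s | 0.26 mm |
| −0.3 (good responders leave) | −0.090 | −0.10 s | −0.15 mm |

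**4. Simulation, Schirmer.** Assumptions: true gain 1.00 mm at each post-baseline visit; SD 1.72 mm per visit; correlation 0.5 to 0.7 between visits; leaving possible only after a visit with no gain, at a rate that loses 15 to 22% before day 90.
- Completers show a mean gain of about 1.15 to 1.26 mm, an overstatement of 0.15 to 0.26 mm.
- If half the leaving is unrelated to response, the bias roughly halves (0.15/2 to 0.26/2, about 0.08 to 0.13 mm).
- If no leaving is related to response, it is zero.
- A likelihood estimate on all attended visits stays within about 0.01 mm of the truth. Leaving here depends only on observed values, which is the condition that estimate needs.

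**5. Simulation of the protocol's own TBUT rule.** Assumptions: baseline TBUT uniform on 5 to 10 s (the range in section 12.1); SD of change 1.1 s; correlation of changes 0.3 to 0.7; true day-90 change 0 to 1 s; removal after any visit with TBUT below 5 s. Between 9 and 18% are removed before day 90, and completers overstate the mean gain by 0.05 to 0.14 s. At correlation 0.5 and no true change, completers show +0.11 s; likelihood analysis of all attended visits shows about 0.00 s.

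**6. Yardstick for arm differences.** With 80 per arm and SD 1.72 mm, the standard error of a difference is 1.72 × √(2/80) = 0.27 mm, and the difference detectable with 80% power is (1.96 + 0.84) × 0.272 = 0.76 mm. The planning difference of 0.13 mm would need 2 × (2.80 × 1.72/0.13)² ≈ 2,745 per group (2,748 with unrounded quantiles), not 80. That is a separate problem, but it makes 0.13 mm an unsafe benchmark here.

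**The case against.** **Scope.** The quoted test covers within-group change only, while the main objective is a comparison with two comparators. A between-group ANOVA run visit by visit uses every partial attender at each visit attended, which is a natural reading of the inclusion rule. The chi-square and Fisher tests do not need complete series either. This stands. A reader might infer that the whole analysis becomes completers-only; the documents do not support that. Deletion of incomplete subjects is also implied by the classical method, not written in section 15, and variants with subject as a factor can be fitted to unbalanced data. Section 15 specifies no such variant.

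**Direction.** Section 12.2.3 lists 14 grounds, many unrelated to response (missed appointments, retinal disease, uveitis, surgery), and no rates by reason are given. The upward direction is therefore conditional. What remains is that the TBUT, added-treatment and insufficient-response grounds all point the same way.

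**Arm differences.** It is tempting to say that the dropout creates a false treatment effect. Simulated losses of about 10% in one arm and 27 to 29% in another do give spurious Schirmer differences of about 0.16 to 0.25 mm. That needs a nearly threefold imbalance, which nothing in the documents supports for three active lubricants; with equal outcome-related loss the bias cancels. Even then it is 0.6 to 0.9 standard errors (0.16/0.27 to 0.25/0.27).

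**Completeness of the remedy.** The efficacy rule in section 14.1 is itself conditional on attending all visits, and a new model leaves that untouched. Section 13 also counts two eyes per subject, which a model must handle. Both points stand.

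**Conclusion.** The gap is real and should be fixed before analysis, but it is limited. Section 15 names a within-group test that, in its classical form, cannot analyse the subjects the same section promises to include, and no stated method closes the gap. Between groups, partial attenders are lost only at the visits they miss, notably day 90.

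Completers may overstate within-arm improvement because some leaving is tied to poor outcome. For Schirmer this is about 0.15 to 0.26 mm on a true 1.00 mm when all leaving follows a visit with no gain, half that when half the leaving is unrelated, and zero when none is related. For TBUT, the elimination rule alone gives 0.05 to 0.14 s. These sizes rest on assumed correlations, loss rates and leaving mechanisms that the documents do not give. The arm comparison is biased only if outcome-related loss differs between arms, and the documents give no ground to expect that.

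**What to change.** For continuous outcomes, replace the repeated-measures ANOVA and the between-group ANOVA in section 15 by one linear mixed model for repeated measures:

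- **Data:** every attended scheduled visit, baseline included, of every randomised subject with at least one post-baseline value. Enter the value at the visit where a subject is eliminated, since that value explains the leaving.
- **Terms:** arm, visit and arm-by-visit, with an unstructured covariance across visits. Use one value per subject or add a term for the two eyes of a subject.
- **Results taken from it:** within-arm changes from baseline and the day-90 arm differences.
- **Sensitivity analysis:** for subjects who leave for insufficient response or added treatment, assign no improvement from baseline at the visits after leaving.
- **Visits:** fit each variable at the visits where it is measured. Section 9 marks the Schirmer test at day 30, but the Visit 2 list in section 11.3 omits it; the two must be reconciled. If section 11.3 is followed, no subject has a full five-visit Schirmer series.

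The cost is a change of analysis wording and slightly more work in standard software, with no new data. The model relies on values being missing at random given the visits attended; the sensitivity analysis addresses part of that reliance.

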### 5.2 *SPECIFIC OBJECTIVES:*

**5.2.1** To evaluate the safety of the preservative-free ophthalmic formulation PRO-087 (by Laboratorios Sophia, S.A. de C.V.) on the corneal and conjunctival epithelium, intraocular pressure, and structures of anterior and posterior segment in patients with tear film dysfunction syndrome from mild to moderate.

**5.2.2** To determine the correlation between improvement of clinical status and perceived improvement of symptoms of each participant in each study group.

**5.2.3** To compare the qualitative and quantitative histological status of the ocular surface before and after the pharmacological intervention in each study group to determine the evolution under the intervention of PRO-087.

**5.2.4** To evaluate the quantitative rating of tear film production by the Schirmer Test throughout the study.

**5.2.5** To qualitatively assess the tear film production by measuring the tear film break-up time stained with fluorescein and cobalt filter.

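### Within-group change in qualitative variables is assigned chi-square or Fisher, which assume independent samples; a paired method should be named for these secondary results

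*Combined protocol and SAP*

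**What the plan says.** Section 15 sets out its tests in this order:

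1. Quantitative variables, within group: "the intra-group differences will be determined by an ANOVA test for repeated measures".
2. Qualitative variables, with no stated scope: a chi-square test, "chi square) test will be used and in case the expected frequencies are less than 5", Fisher's exact test.
3. Between groups: "The differences between groups will be analyzed using the ANOVA test for variance analysis".
4. Qualitative variables again: "For qualitative variables, contingency tables 2x2 will be used and the differences will be calculated with" a Yates-corrected chi-square, or Fisher when expected counts are small.

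The error level is common to all tests: "The significance level will be of a 0.05 alpha value or less".

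A within-group, before/after comparison of qualitative data is an explicit aim. Objective 5.2.3 reads: "To compare the qualitative and quantitative histological status of the ocular surface before and after the pharmacological intervention in each study group". The schedule in section 9 takes impression cytology at baseline and day 90 in the same subjects. No paired categorical method (McNemar, Wilcoxon signed-rank, Cochran's Q, a clustered model) is named anywhere in the document.

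**The concern.** Chi-square and Fisher compare proportions from two separate sets of people. Here the two sets are the same people at two times. The plan respects that pairing for quantitative variables and drops it for qualitative ones.

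The chi-square variance leaves out the covariance between a subject's two values. If that covariance is positive, the standard error is too large: p-values are too big, the test rejects less often than its nominal level, and real change within an arm is harder to detect. What is at stake is the qualitative half of objective 5.2.3 and any other within-arm p-value that the analysts choose to compute for a sign or grade.

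**Working it through.** **Which comparison the sentence governs.** It does not itself say within-group. It follows directly on the within-group ANOVA, and the between-group block that comes next has its own qualitative test. Read as between-group, it would duplicate that later sentence, conflict with it on Yates's correction, and leave objective 5.2.3 with no qualitative test. The within-group reading is the likely one.

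**Inputs.** From the plan: alpha 0.05 (section 15); z = 1.96, so two-sided (section 13); 80 subjects per group before losses and 96 planned (section 13.3). Assumed, because the documents give no values: one record per subject, the rates of the sign, and the within-subject correlation phi. The plan states no power or rate for these tests, so there is no figure to reproduce.

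**Type I error.** With rate p at both times and n subjects, the chi-square test uses the variance 2p(1 − p)/n for the difference. The true variance is 2p(1 − p)(1 − phi)/n. Under no change the true error is therefore about 2[1 − Φ(1.96/√(1 − phi))]:

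| phi | 1.96/√(1 − phi) | true type I error |
|---|---|---|
| 0 | 1.960 | 0.050 |
| 0.1 | 2.066 | 0.039 |
| 0.3 | 2.343 | 0.019 |
| 0.5 | 2.772 | 0.006 |
| 0.7 | 3.578 | 0.0003 |

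A negative correlation of −0.2 would give 0.074, so the direction depends on the sign of phi.

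**Power, fall from 50% to 35%.** The probability of the sign at both times is p11 = p0·p1 + phi·√[p0(1 − p0)p1(1 − p1)]. At phi 0.5 this is 0.175 + 0.5 × 0.5 × 0.477 = 0.294, which leaves 0.206 who lose the sign, 0.056 who gain it and 0.444 with neither. Power is the total multinomial probability of the paired tables that each test rejects at two-sided 0.05. Simulation with 20,000 trials per setting agrees to within about a percentage point.

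| n | phi | chi-square as planned | exact McNemar | mid-p McNemar |
|---|---|---|---|---|
| 80 | 0.1 | 47% | 45% | 51% |
| 80 | 0.3 | 47% | 55% | 61% |
| 80 | 0.5 | 46% | 71% | 77% |
| 80 | 0.7 | 45% | 95% | 97% |
| 96 | 0.3 | 57% | 64% | 70% |
| 96 | 0.5 | 58% | 80% | 84% |
| 96 | 0.7 | 59% | 98% | 99% |

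**One illustrative table, n = 96.** Sign present in 48 at baseline and 36 at day 90; 18 subjects lose it, 6 gain it, 30 have it both times and 42 neither time. The phi of this table is (30/96 − 0.5 × 0.375)/√(0.25 × 0.234) = 0.52.

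- Chi-square: pooled rate 84/192 = 0.4375; standard error √(0.4375 × 0.5625 × 2/96) = 0.0716; z = 0.125/0.0716 = 1.75; p = 0.081.
- Exact McNemar: 2 × P(X ≤ 6), X binomial(24, 0.5); p = 0.023.

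The same data fall on opposite sides of 0.05.

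**The other possible layout.** If the analyst cross-tabulated baseline against final status, chi-square would test association, not change. With no true change, n = 96 and phi 0.3, it rejects in about 84% to 86% of simulated trials (rates of 30% and 50%). Neither layout gives a valid test of change.

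**The case against.** The case for leaving this alone, or ranking it low, has real substance.

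- **The correlation is unknown.** The documents give neither phi nor baseline rates. At phi of about 0.1 or below nothing much is lost, and exact McNemar is then slightly weaker than the planned test (45% against 47% at n = 80). This stands. It limits the size of the effect but does not make an independent-samples test valid.
- **The net direction is not certain.** Section 13 also counts eyes (576). Analysing eyes as independent records would add an error in the anti-conservative direction. This stands, and it is why the figures are tied to one record per subject.
- **The scope is narrow.** Only objective 5.2.3 explicitly asks for a qualitative within-group comparison. The stated focus of the cytology is goblet-cell density and amount (section 10.4), which is quantitative and goes to ANOVA. No section assigns a within-arm significance test to Oxford grade, hyperemia, burning, foreign body sensation or tearing. This stands.
- **The scope of the sentence is inferred from its position.** True. But under the alternative reading the plan has no within-group qualitative test at all, so the text still needs correcting.

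A reader might infer that worsening tolerability would be hidden. The documents do not support that: sections 14.2 to 14.3.1 judge tolerability and safety by fixed proportions and limits, such as a symptom recorded as absent in 95% of subjects, and no within-arm p-value enters those rules.

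**Conclusion.** The concern holds for secondary results. As the sentence most naturally reads, section 15 assigns a test for independent samples to paired qualitative data, and the resulting p-values are not valid for within-group change.

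With one record per subject and positive correlation, the test is conservative: the true error falls from about 0.04 at phi 0.1 to about 0.0003 at phi 0.7. For a fall from 50% to 35% in 80 subjects, the power lost against exact McNemar is about 8 percentage points at phi 0.3 (47% against 55%), 25 at phi 0.5 (46% against 71%) and 50 at phi 0.7 (45% against 95%). Near phi 0.1 there is little or no loss.

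It would go too far to conclude that real change will often be missed, or that the trial's main conclusion is at risk. The first depends on a correlation that the documents do not give. The second does not follow, because the main objective is the comparison with the two Systane products, the between-arm tests are untouched, and the sample size rests on TBUT, OSDI and Schirmer. This is a correction that should be made, not one on which the trial stands or falls.

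**What to change.** In section 15, label the first qualitative sentence as within-group and replace its tests:

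- Present/absent items: McNemar's test, mid-p or exact, with the choice stated in advance. Mid-p is the more powerful of the two in the settings above.
- Ordinal grades such as Oxford or hyperemia: Wilcoxon signed-rank or Stuart-Maxwell.
- Several visits, or both eyes: a logistic or ordinal GEE or mixed model clustered on subject.
- Chi-square and Fisher: keep for between-arm tables only.

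The cost is a few lines of analysis wording. The data, visits and sample size do not change. The change should be made before unblinding, so that the choice of a paired test cannot look driven by the results.
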